H	DATA HANDLING AND RECORD KEEPING	12
H1	CONFIDENTIALITY AND SECURITY	13
H2	TRAINING.....	13
H3	CASE REPORT FORMS AND SOURCE DOCUMENTS.....	13
H4	RECORDS RETENTION	13
H5	PERFORMANCE MONITORING.....	13
I	STUDY MONITORING, AUDITING, AND INSPECTING	13
I1	STUDY MONITORING PLAN.....	13
I2	AUDITING AND INSPECTING	13
J	STUDY ADMINISTRATION	13
J1	ORGANIZATION AND PARTICIPATING CENTERS.....	13
J2	FUNDING SOURCE AND CONFLICTS OF INTEREST.....	13
J3	COMMITTEES	13
J4	SUBJECT STIPENDS OR PAYMENTS	13
J5	STUDY TIMETABLE	14
K	PUBLICATION PLAN	14
L	ATTACHMENTS	14
L1	TABLES	14
L2	INFORMED CONSENT DOCUMENTS.....	14
L3	PATIENT EDUCATION BROCHURES	14
L4	SPECIAL PROCEDURES PROTOCOLS	14
L5	QUESTIONNAIRES OR SURVEYS.....	14
M	REFERENCES	15

A Introduction

A1 Study Abstract

Auditory training as the potential to dramatically affect older persons' adjustment to a new hearing aid and to maximize the benefits they receive from wearing one. In turn, by wearing hearing aids, they experience easier and more successful communication patterns. They enhance their ability to engage in everyday conversations and will be able to become more socially involved with their family and friends. In this study we will try to determine the extent to which web-based cLEAR auditory brain training, with concomitant support from a cLEAR in-house audiologist, affects satisfaction with new hearing aids and increases daily use time. Thirty adults over the age of 60 years will receive new hearing aids for the first time. After an adjustment period, half will complete cLEAR's auditory brain training program right away and the other half will complete it after a delay period, and both will complete a control condition. To establish the level of feasibility and clinical utility we will measure hearing aid satisfaction, benefit ratings, and hearing aid use time.

A2 Primary Hypothesis

Use of the web-based cLEAR auditory brain training system with concomitant support from a cLEAR in-house audiologist improves satisfaction with new hearing aids and increases daily use time.

A3 Purpose of the Study Protocol

Determine the extent to which web-based cLEAR auditory brain training with concomitant support from a cLEAR in-house audiologist affects satisfaction with new hearing aids and increases daily use time.

B Background

B1 Prior Literature and Studies

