Patients want regular contact with an audiologist. In a study of 93 adults (mean age=66 years, SD=17), we asked the question, what did you like best about the auditory training ([name] et al., 2012). One of the three top answers was "regular contact with an audiologist". The other two were "the games were fun to play" and "training gave me empowerment over my hearing loss." By completing auditory brain training, participants also reported increased confidence to engage in everyday conversations.

C Study Objectives

C1 Primary Aim

It is the objective of this study to determine if the use of cLEAR following a first-time hearing aid fitting will increase satisfaction and daily hearing aid use.

C2 Secondary Aim

N/A

C3 Rationale for the Selection of Outcome Measures

1. Primary outcome measures are questionnaires used in hearing clinics to assess hearing aid satisfaction.
2. Hearing aids log use time. This information will also be collected to determine the average daily use time for each participant.

D Investigational Agent

D1 Preclinical Data

N/A

D2 Clinical Data to Date

N/A

D3 Dose Rationale and Risk/Benefits

N/A

E Study Design

E1 Overview or Design Summary

All qualified participants will first be fitted with one hearing aid using manufacturer recommended settings. The settings will be verified using real-ear measurements and any initial adjustments to the hearing aid will be made at the time of fitting. The participants will return again in 2-3 weeks to complete any final adjustments needed before they continue with the protocol.

After fitting and final adjustments are complete, all participants will be receive aided speech perception testing using the Speech in Noise Test (SPIN) and the NU-6.

Half of the participants will be assigned to the Early Group and receive 8 hours of cLEAR auditory brain training in 20 minute intervals spread over four weeks. The other half will be assigned to the Late Group and receive the cLEAR training after

a four week control period. The Early Group will do the control period after their training period.

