Lists of potential participants will be obtained from multiple sources including the Washington University's Volunteers for Health program and from an extensive database maintained in the [name] lab. Potential participants will hear about the study and complete a health and hearing screening questionnaire over the telephone. If they pass the telephone screening, they will be asked to come to the hearing lab for the hearing and vision assessment. The hearing screening will include pure-tone threshold testing and speech perception testing at comfortable levels.

To be enrolled in the study potential participants will have bilateral mild to severe sensori-neural hearing loss, and have never used hearing aids. They will also require the basic skills for wearing and maintaining a hearing aid including the manual dexterity to insert the aid and the anatomy required to wear the aid. They will also have corrected static visual acuity of 20/40 or better. They will be required to pass a dementia screener (MMSE). If they qualify for the study and wish to continue they will be consented after completing the assessments. Those that do not qualify will be paid for their time and any collected data destroyed.

2.d Randomization Method and Blinding

Because participants act as their own control per se, they will not be randomized and no blinding will occur.

2.e Risks and Benefits

There are no foreseeable risks to the participant beyond the basic risks associated with hearing aid fitting. These risks are rare but include possible skin irritation from the device or the occasional uncomfortably loud sound. Hearing aids are equipped with safety mechanisms that are supposed to reduce the possibility that a very uncomfortable level is produced.

The participant will participate in a study that provides amplification and auditory training. These devices and procedures are designed to be of benefit to individuals with hearing loss. The participants will also be providing feedback on their experiences. This feedback may improve the procedures and methods currently used in online auditory training practices, this may benefit society.

2.f Early Withdrawal of Subjects

Participants that have not completed the study but can no longer participate will be asked to return the hearing aid. They will be reimbursed for their time at 10\$/hour.

2.g When and How to Withdraw Subjects

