If it is deemed that they can no longer fulfill the needs of the study because they are not training or coming to the in-clinic assessments participants will be notified by phone or email if they are to be withdrawn from the study.

2.h Data Collection and Follow-up for Withdrawn Subjects

There will be no follow-up with withdrawn participants.

E3 Study Drug

3.a Description

N/A

3.b Treatment Regimen

N/A

3.c Method for Assigning Subjects to Treatment Groups

N/A

3.d Preparation and Administration of Study Drug

N/A

3.e Subject Compliance Monitoring

N/A

3.f Prior and Concomitant Therapy

N/A

3.g Packaging

N/A

3.h Blinding of Study Drug

N/A

3.i Receiving, Storage, Dispensing and Return

N/A

F Study Procedures

F1 Screening for Eligibility

A telephone survey will screen all potential participants that would not be eligible for reasons other than the hearing and vision screening. Hearing and vision testing will be conducted after the informed consent process.

F2 Schedule of Measurements

F3 Visit 1

F4 Visit 2 etc.

F5 Safety and Adverse Events

5.a Safety and Compliance Monitoring

5.b Medical Monitoring

- i **Investigator only**
- ii **Independent expert to monitor**
- iii **Institutional Data and Safety Monitoring Board**
- iv **Independent Data and Safety Monitoring Board**

5.c Definitions of Adverse Events

5.d Classification of Events

- i **Relationship**
- ii **Severity**
- iii **Expectedness**

5.e Data Collection Procedures for Adverse Events

5.f Reporting Procedures

5.g Adverse Event Reporting Period

5.h Post-study Adverse Event

F6 Study Outcome Measurements and Ascertainment

G Statistical Plan

G1 Sample Size Determination and Power

We determined the power to detect an effect size for differences as large as or larger than in [name] et al. (mean = .733, SD = .783) with an alpha level of .05 will exceed .95 using a one-tailed test for the within-subjects comparisons in each group.

G2 Interim Monitoring and Early Stopping

We will monitor progress in the software to be sure participants are following protocol.

G3 Analysis Plan

We will assess the effect of training on hearing aid use time, changes in speech perception, and subjective changes indicated by the questionnaire rating-scale responses. Three post-fitting times will be assessed to look at the effects of CLEAR testing (Baseline/post-fitting, post-training, post control, and four weeks post intervention).

G4 Statistical Methods

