Data will be analyzed with t-tests and repeated measures ANOVA.

G5 Missing Outcome Data

Participants with missing data will not be included in the analyses for that outcome measure.

G6 Unblinding Procedures

N/A

H Data Handling and Record Keeping

H1 Confidentiality and Security

H2 Training

H3 Case Report Forms and Source Documents

H4 Records Retention

H5 Performance Monitoring

I Study Monitoring, Auditing, and Inspecting

I1 Study Monitoring Plan

I2 Auditing and Inspecting

J Study Administration

J1 Organization and Participating Centers

J2 Funding Source and Conflicts of Interest

INCLUDE INFO FROM CIRC? BUT WE ARE NOT THE PI, SO IT WOULDN'T MAKE SENSE HERE.

J3 Committees

J4 Subject Stipends or Payments

Participants will be paid \$10/hour for the time spent in assessments and training.

Other - The project involves first time hearing aid users. We need to control for the level of technology and hearing aid quality across participants, so the hearing aid will be provided. The aid will be 'used' after the study so the participant will be allowed to keep the aid after the study is complete.

J5 Study Timetable

K Publication Plan

L Attachments

L1 Tables

L2 Informed consent documents

Adult SBIR HA and AT Informed consent.rtf	Consent & Assent Forms	1	407 k	E	08/20/19
--	------------------------	---	-------	---	----------

L3 Patient education brochures

L4 Special procedures protocols

L5 Questionnaires or surveys

Attachment Name	Category	Ver	Size		Attached
JIT Letter.doc	Notice of Just in Time (JIT) Documentation	1	25 k	E	08/15/19
Telephone	Recruitment Script: Phone	1	59 k	E	08/19/19

Questionnaire.rtf					
AT and HA Flier.rtf	Recruitment Materials: Ads/Brochures/Posters/News Release/Fliers	1	115 k	E	08/19/19
COSI.pdf	Subject Data Collection Instruments	1	36 k	E	08/21/19
Demographic - Case History Form.rtf	Subject Data Collection Instruments	1	86 k	E	08/20/19
Email and Phone Script for Followups.doc	Subject Data Collection Instruments	1	23 k	E	08/20/19
IOI-HA.pdf	Subject Data Collection Instruments	1	37 k	E	08/21/19
SADL Form.pdf	Subject Data Collection Instruments	1	58 k	E	08/21/19
Assurance Form Signed.pdf	Assurance Document	1	226 k	E	08/21/19

M References

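### No time point is set for reading the hearing-aid use log, and none when a withdrawn participant returns the aid, so use time up to withdrawal may go unused

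*Protocol*

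**What the plan says.** The primary hypothesis (Protocol A2) is that training "improves satisfaction with new hearing aids and increases daily use time", and the single aim (C1) names the same two outcomes. On the source of the use data, C3 says: "Hearing aids log use time. This information will also be collected to determine the average daily use time for each participant". So collection is planned for each participant.

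The protocol does not say when or how it happens. The end-of-period assessments in E1 are the speech tests and the questionnaires, and a log reading is not among them. F2 (schedule of measurements), F3, F4 and F6 are headings without text.

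For people who stop early, 2.f says "Participants that have not completed the study but can no longer participate will be asked to return the hearing aid" and adds only payment for time. Section 2.h, whose heading covers data collection as well as follow-up for withdrawn subjects, consists of one sentence: "There will be no follow-up with withdrawn participants". G5 then sets the missing-data rule: "Participants with missing data will not be included in the analyses for that outcome measure". G4 plans t-tests and repeated measures ANOVA. The SAP compares change during training with change outside training.

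**The concern.** Questionnaire scores not obtained before a person leaves are gone. Use time differs, because the record sits in a device that the protocol asks to have back. If nobody is told to read it, an obtainable measurement becomes missing, and G5 removes the person from the use-time analysis. Changing the analysis rule later cannot restore a log that was never read, so this is a collection step as well as an analysis rule.

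Who is removed also matters. Section 2.g withdraws people who are not training or not attending assessments. Disengagement of that kind could plausibly go with wearing the aid less, and people who miss visits would also miss any reading made there. Exclusion could then be selective for the outcome under study.

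**Working it through.** **The plan's own figure.** The only sizing figure is the power statement in G1 and the SAP: mean 0.733, SD 0.783, one-tailed alpha 0.05. With d = 0.733/0.783 = 0.936 and 15 per group (30 split in half), a paired t-test has power 0.964. This agrees with G1's claim of more than .95. The SAP bases the effect on the COSI, so it says nothing about use time. The documents give no use-time effect, SD or withdrawal rate.

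**What a leaver could contribute to a training-versus-control contrast**, if the log were read:

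| Leaves during | Use data available | Contrast |
|---|---|---|
| First period | Part of one condition | None; descriptive only |
| Second period | All of the first condition, part of the second | Possible, less precise |
| Final four weeks | Both conditions in full | Possible in full |

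The second row has a condition. First-period use must be separable from second-period use, which needs either a reading at the end of the first period or a log that stores dated use. The documents do not describe the log. If a first-period reading exists, those data are already in hand and only the analysis rule excludes them.

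**Precision.** Assume 10% to 20% withdrawal, so 27 to 24 of 30 remain. The standard error is proportional to 1/√n:
- √(30/27) = 1.054, or 5% wider
- √(30/24) = 1.118, or 12% wider

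These are upper limits on what could be recovered. They treat every leaver as supplying a full contrast, whereas first-period leavers supply none and partial periods carry less information.

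**Level of use.** If a proportion p leaves and wears the aid g hours a day less than completers, the completers' mean exceeds the mean of all participants by p × g. Assuming p of 0.10 to 0.20 and g of 2 to 4 hours:
- 0.10 × 2 = 0.2 h
- 0.20 × 4 = 0.8 h

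This concerns mean daily use, not the training effect. In a within-person contrast a common shortfall cancels: (training use − g) − (control use − g) = training use − control use. The contrast is biased only if leavers' training effect differs from completers', and the documents give no basis for a figure.

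**The case against.** The strongest reply is that C3 already commits to collecting log data for each participant, without an exception for those who withdraw, and that reading a device already handed back is not clearly follow-up under 2.h. That stands in part. A reader might infer that no log is ever read, or that leavers' data are certain to be lost. The documents support neither. They are silent on a reading at return and do not rule one out. What is missing is a stated time point and procedure, for completers as well as leavers.

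Second, return of the aid is requested, not assured. People withdrawn under 2.g for non-attendance are told by phone or email, and no return procedure is given. It would go too far to say that the sponsor holds every leaver's log.

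Third, reading the log does not by itself keep anyone in the analysis. Repeated measures ANOVA on complete cases needs every time point, so G4 and G5 must change too. This stands, and the fix has to cover it.

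Fourth, C3 states: "Primary outcome measures are questionnaires used in hearing clinics to assess hearing aid satisfaction". Use time is half of the hypothesis, but C3 does not label it a primary outcome measure. This limits the weight of the point without removing it.

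**Conclusion.** The point holds as a gap in procedure combined with an exclusion rule. No reading time is stated, 2.f and 2.h provide no reading at device return, and G5 drops the person. Use time up to withdrawal may therefore go unused for an outcome that the hypothesis names.

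The gain from closing the gap is less selective exclusion and some precision: at most 5% to 12% in the standard error, assuming 10% to 20% withdrawal. A reader might take the 0.2 to 0.8 h above as bias in the estimated training effect. It is not. It rests on assumed inputs and describes the level of use among completers. This is a cheap improvement to the plan, not a demonstrated flaw in the planned comparison.

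**What to change.** 1. **Schedule (E1 or F2).** State that the use log is read at each end-of-period visit and whenever an aid is returned. G3 counts a baseline time, so a reading at the post-fitting visit would also separate the adjustment weeks from the first period.
2. **Withdrawal (2.f and 2.h).** State that the log of a returned aid is read, that use time up to the withdrawal date is entered for each period reached, and that this is not follow-up in the sense of 2.h.
3. **Analysis (G4, G5 and SAP), for use time only.** Replace the complete-case exclusion with an analysis of all available periods. This can be a paired training-versus-control contrast for everyone with data in both periods, or a mixed model in place of complete-case repeated measures ANOVA. Report first-period leavers descriptively.
4. **Running averages.** If the log gives only an average since the last reading, use it for the period in progress only where days after withdrawal can be separated out. Otherwise unworn days before return would understate use, and that period should be treated as missing.

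The cost is a few sentences and a few minutes per reading. No visit is added beyond those planned and the return already requested. Last periods will sometimes be partial, some aids will not come back, and consent wording must cover device data recorded before withdrawal. A mixed model also assumes that missingness is explained by the use already observed, which should be stated.

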“AUDITORY BRAIN TRAINING TO ENHANCE SATISFACTION AND USAGE OF NEW HEARING AIDS BY OLDER ADULTS”

NCT04230876

Document Date/Version: 6/15/22

Data will be analyzed with Repeated measures ANOVA to assess the effect of training on use time, changes in speech perception, and subjective changes indicated by the questionnaire rating-scale responses. Repeated measures will compare changes in outcome measures for the time spent during training to changes during the time spent not in the training. The numbers of participants in each group was determined based on effect sizes for the COSI in [name] et al. (2016), who found differences post-training using the same primary outcome measure, a similar training schedule and similar methods proposed here. We determined the power to detect an effect size for differences as large as or larger than in [name] et al. (mean = .733, SD = .783) with an alpha level of .05 will approach .95 using a one-tailed test for the within-subjects comparisons.

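### G1 powers one-tailed tests inside each group, while the SAP's training versus non-training comparison is not stated as pooled, adjusted for period or limited to the audiobook period

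*Protocol*

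**What the plan says.** Protocol A1 sets the size: "Thirty adults over the age of 60 years will receive new hearing aids for the first time". Section 2.c confirms that they "have never used hearing aids". Under E1, half form the Early Group (training, then the audiobook control period) and half the Late Group (the reverse). A further four-week period follows. Section 2.d rules out randomisation.

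G1 takes a mean difference of .733 and SD of .783 from a cited earlier study and claims power above .95 "using a one-tailed test for the within-subjects comparisons in each group". G4 names t-tests and repeated measures ANOVA without listing factors, G3 labels the assessment times by condition, and G5 drops participants with missing data from the outcome concerned.

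The SAP gives the only explicit contrast: "Repeated measures will compare changes in outcome measures for the time spent during training to changes during the time spent not in the training". On size it says: "The numbers of participants in each group was determined based on effect sizes for the COSI". Its power statement is that power "will approach .95 using a one-tailed test for the within-subjects comparisons", without G1's closing reference to each group. Neither document says that Early and Late are pooled, names a period or sequence term, or says whether the final four weeks count as non-training time.

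**The concern.** People wearing a first hearing aid may go on adapting after the baseline visit, whether or not they train. Inside one group, training and calendar period coincide completely, so a test confined to that group cannot tell them apart without an assumption about adaptation.

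A positive result in Early could then be adaptation. If the in-group test is a contrast of changes and adaptation slows, a real effect in Late could be hidden, and the two groups could appear to disagree about the same training. The design contains the information to avoid this, because the two orders mirror each other. The plan does not commit to the analysis that uses it.

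**Working it through.** **Inputs.** From the documents: mean .733, SD .783, one-tailed alpha .05, 30 participants in two halves (15 v 15). Assumed, because the documents give none: adaptation P1, P2, P3 in the three periods, the correlation r between a participant's two period changes, and losses per group. T is the training effect.

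**1. G1's figure.** Standardised effect .733/.783 = .936. A one-sided paired t-test (noncentral t, n - 1 df) gives .937 at n = 13, .952 at n = 14, .964 at n = 15 and above .999 at n = 30. G1's claim therefore reproduces for one group of 15, and needs at least 14 complete cases in that group. It does not describe the pooled 30.

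**2. What each test estimates, with training gains retained.**

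| Test | Early | Late |
|---|---|---|
| Pre-post over training | T + P1 | T + P2 |
| Training change minus control change | T + (P1 - P2) | T - (P1 - P2) |
| Equal-weight average of the second row | T | T |

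**3. In-group error, n = 15, no training effect.** The SD of the contrast of changes is .783 x sqrt(2(1 - r)): 1.356, 1.107 and .783 at r = -.5, 0 and +.5. The value -.5 arises when visit errors are independent with equal variance. The table takes P2 = 0, so P1 is also the difference.

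| P1 | Early pre-post | Early contrast, r = -.5 | Late contrast, r = -.5 |
|---|---|---|---|
| .1 | 12% | 8% | 2.8% |
| .3 | 41% | 20% | 0.7% |
| .5 | 76% | 39% | 0.1% |

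Late's pre-post test stays at 5% here because P2 = 0. With a true effect of .733, P1 = .3 and r = -.5, the in-group contrast has power .88 in Early and .32 in Late, against .64 in each without adaptation.

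**4. SAP contrast pooled over all participants, no period term.** The bias is (nE - nL)/(nE + nL) x (P1 - P2). Type I error is simulated at r = -.5 with a difference of .3:
- 15 v 15: bias 0, about 4.6%.
- 15 v 13: 2/28 x .3 = .02, between 5.3% and 5.5%.
- 15 v 11: 4/26 x .3 = .046, about 6.4%; a true .733 is estimated as .78.
- 11 v 15: bias -.046, about 3.2%.

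With a period term the error is about 5% in the 15 v 15, 15 v 11 and 11 v 15 cases.

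**5. Final four weeks averaged into the comparator.** Early gives P1 - (P2 + P3)/2 and Late gives P2 - (P1 + P3)/2. Their average is (P1 + P2)/4 - P3/2. At (.3, 0, 0) the bias is .3/4 = .075 and type I error about 9.5%, and a period term does not remove it (9.8%). At (.3, .2, .1) the bias is .5/4 - .05 = .075. At (.3, .1, .2) it is .4/4 - .1 = 0.

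**6. Power of the equal-weight contrast against the audiobook period.** At 15 v 15 the standard error is SD/sqrt(30) on 28 df.

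| r | SD | One-sided power, 15 v 15 | 15 v 11 |
|---|---|---|---|
| -.5 | 1.356 | .89 | .84 |
| 0 | 1.107 | .97 | .95 |
| +.5 | .783 | above .99 | above .99 |

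**7. Fading.** If a fraction f of the gain is lost by the end of Early's control period, Early estimates T(1 + f), and the average is T(1 + f/2): .733 x 1.125 = .82 at f = .25 and .733 x 1.25 = .92 at f = .5.

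**8. Baseline.** Section E1 lists only SPIN and NU-6 after the final fitting adjustments and places the questionnaires at the end of each period. G3 lists a post-fitting baseline. Without a COSI score at that visit, first-period change on the COSI is undefined.

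**The case against.** G1 is a power statement, and the SAP holds the only defined contrast. That contrast is naturally read as pooled: G3 labels times by condition, section 2.a says the groups differ only in schedule, and the SAP's power sentence drops the reference to each group. Pooled over 15 v 15 and limited to the training and audiobook periods, it is not inflated. G1 also leaves its comparison undefined; if it means training change minus control change, equal adaptation in both periods cancels even inside one group. The adjustment phase may reduce the problem: "The participants will return again in 2-3 weeks to complete any final adjustments needed before they continue with the protocol". All of this stands, although nothing shows that adaptation is complete by then.

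A reader might infer that the trial cannot separate training from adaptation, or that its false-positive rate is 41% or 76%. The documents support neither. Those rates belong to Early's pre-post test alone, under assumed adaptation. With P2 = 0, if success required both groups (a possible but unstated reading), the joint rate at .3 would be .408 x .05 = 2%.

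The objection does not supply what is missing. Pooling is never stated, the powered test is the per-group one, and the comparator is open to the final four weeks. The imbalance effect is modest, and 15 v 11 puts four losses all in one group.

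**Conclusion.** The power arithmetic in G1 is correct, but it is stated for tests inside each group, which isolate training only under an assumption about adaptation that the documents do not make. The SAP's contrast is sound at 15 v 15 if pooled and limited to the audiobook comparator. It becomes mildly biased when exclusions unbalance the groups, and can be biased by about +.075 if the final period counts as control. This is a should-fix clarification, and not evidence that the planned analysis is invalid. The direction of each bias follows from the design, while every size rests on assumed adaptation, correlation and losses.

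**What to change.** In G1, G3, G4 and the SAP, make the confirmatory test one pooled contrast: each participant's change over the training period minus change over the audiobook control period, averaged with equal weight over Early and Late. This is equivalent to adjusting for period. Apply it to the COSI, and in the same form to daily use time, since A2's hypothesis is that training "improves satisfaction with new hearing aids and increases daily use time". Keep in-group results as descriptive, and report the final four weeks separately as retention.

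Reconcile E1 with G3 so that the COSI and the other questionnaires have a post-fitting baseline. Replace the differing power statements in G1 and the SAP with power for this contrast over a stated range of correlations.

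The cost is one degree of freedom, revised wording, and questionnaires at the post-fitting visit if they are not already given there; the number of participants and the schedule can stay. The price to name openly is that stated power may fall below .95 if the two changes are negatively correlated (.89 at -.5).

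Two limits remain and should be written down: the contrast assumes that gains do not fade during Early's control period, and that the non-randomised groups adapt alike.
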